1.0 BACKGROUND AND RATIONALE

1.1 Study Synopsis

This will be a single arm, uncontrolled, non-blinded study of PAE using HydroPearl Beads in a small population of 30 subjects with benign prostate hyperplasia (BPH) to investigate the effectiveness of prostatic artery embolization (PAE) relative to previous medication alone for reducing urinary symptoms due to BPH. Secondary aims will be to assess adverse effects of medication vs adverse events secondary to PAE as well as Quality of Life scores on medication vs after PAE.

1.2 Disease Background

Over the past 7 years, data has emerged from numerous countries supporting the safety and efficacy of prostatic artery embolization (PAE) for the treatment of lower urinary tract symptoms (LUTS) in the setting of benign prostatic hyperplasia (BPH) (1). In response, the Food and Drug Administration (FDA) recently granted a de novo classification to Merit Medical Systems to expand the indications for Embosphere Microspheres to include PAE for the treatment of BPH. Moreover, it has given 510(k) clearances to both Embozene Microspheres and HydroPearl Microspheres.

Medication is the first line therapy for lower urinary tract symptoms (LUTS) secondary to BPH. These medications include alpha-adrenergic inhibitors, 5-alpha reductase inhibitors and phosphodiesterase inhibitors. While these medications are effective in improving urination in many men, there are also troubling side effects including retrograde ejaculation, erectile dysfunction, gynecomastia, lightheadedness, nasal congestion and loss of libido. Because of these side effects many men will discontinue the use of these medications.

It has been shown that PAE is very unlikely to result in a major complication and the minor complications tend to resolve without treatment within several weeks of the procedure. Therefore, because of its safety, and the untoward effects of BPH medications, it may be reasonable to suggest that PAE could be substituted as first line treatment for BPH. To further explore this notion, research comparing PAE to medication is needed.

2.0 STUDY OBJECTIVES

2.1 Primary Objective

The primary aim of this study is to determine if PAE will result in a reduction of urinary symptoms similar to medication in individual patients.

2.2 Secondary Objectives

The secondary aims are to determine if PAE will result in less adverse events compared to medication in individual patients and to determine if self assessed quality of life is better on medication or after PAE.

2.3 Outcome Variable

2.3.1 Primary Study Outcome Variable

Reduction in IPSS at 6-month follow-up.

2.3.2 Secondary Study Outcome Variable

1. Improvement of QoL score at 6 months
2. Improvement of uroflowmetry (Qmax, PVR) at 6 months
3. Reduction of prostate volume at 6 months
4. Percentage of prostate infarcted at 6 months
5. Incidence of adverse events at 3 months

3.0 PATIENT ELIGIBILITY

Study subjects will be men with benign prostatic hyperplasia who have been taking an alpha-blocker, a 5-alpha reductase inhibitor or both for at least 6 months.

Thirty (30) subjects will be enrolled and all are anticipated to complete the study.

3.1 Inclusion Criteria

Subjects must meet all of the inclusion criteria to participate in this study.

3.1.1 Male

3.1.2 Age \geq 40

3.1.3 Prostate gland measures \geq 50 grams measured by MRI, CT, or ultrasound

3.1.4 Currently taking BPH medications including either alpha blockers, 5-alpha reductase inhibitors or the combination of both for no less than 6 months

3.1.5 Capable of giving informed consent

3.1.6 Life expectancy greater than 1 year

3.2 Exclusion Criteria

All subjects meeting any of the exclusion criteria at baseline will be excluded from study participation.

3.2.1 Severe vascular disease as defined by severe arterial calcification seen on prior imaging, history of lower extremity or pelvic bypass grafts or history of lower extremity or pelvic arterial stenting. For patients that do not have prior imaging at

UNC, we will rule out suspected severe arterial calcification given their medical history.

- 3.2.2** Uncontrolled diabetes mellitus which is defined as A1C >8%
- 3.2.3** Patients currently taking SGLT2 inhibitors (cana-, dapa-, empa-, and ertugliflozin) due to their diuretic effects
- 3.2.4** A smoking history of 20 pack-year or greater obtained by patient report
- 3.2.5** Prior myocardial infarction
- 3.2.6** A stroke within the last 6 months
- 3.2.7** Unstable angina
- 3.2.8** Immunosuppression
- 3.2.9** Neurogenic bladder and/or sphincter abnormalities secondary to Parkinson's disease, multiple sclerosis, cerebral vascular accident, diabetes, etc.
- 3.2.10** Complete urinary retention
- 3.2.11** Impaired kidney function (serum creatinine level > 1.8 mg/dl or a glomerular filtration rate < 60 as approximated using serum creatinine levels) unless anuric and on dialysis.
- 3.2.12** Confirmed or suspected bladder cancer as assessed based on patients' medical history or current hematuria
- 3.2.13** Urethral strictures, bladder neck contracture, or other potentially confounding bladder pathology
- 3.2.14** Ongoing urogenital infection. For patients with symptoms of a urogenital infection (dysuria, fever, etc.), a urinalysis will be obtained.
- 3.2.15** Previous pelvic radiation or radical pelvic surgery
- 3.2.16** Confirmed malignancy of the prostate or a history of prostate cancer
- 3.2.17** Contrast hypersensitivity refractory to standard medications (antihistamines, steroids)

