4.1.6 Screening Visit (Visit 1)

If a patient qualifies to be a subject in the study based on the inclusion and exclusion criteria listed in section 3.1 and 3.2, the study coordinator will be notified. The coordinator will review the study with the patient and obtain written informed consent. Once the subject is enrolled in the study, he will be seen by one of the co-investigators in either the IR or Urology clinics at one of the study sites. The procedure will be again described to the patient and any questions will be answered. International Prostate Symptoms Survey (IPSS) with Quality of Life (QOL) questionnaires and Qmax and PVR measurements will be obtained if not completed in the prior 3 months during the pre-study work-up. Study specific questionnaires to assess medication usage will also be completed. A MRI of the pelvis with and without contrast will be ordered and obtained prior to visit 2 for baseline evaluation of the prostate unless the patient has one from the prior 6 months. If the patient had a contrast enhanced MRI of the pelvis within the past 6 months, this MRI will be used.

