5.4 Expected Risks

A recent meta-analysis of PAE data from 662 patients in nine studies reported only two major complication (0.3% major complication rate) involving bladder ischemia requiring surgery and severe urinary sepsis requiring hospitalization. Among minor complications transient rectal pain and/or dysuria (9.1%), acute urinary retention (7.9%) and transient hematuria (4.4%) were the most common (1).

Detailed risk analysis is below:

	Risk or Side Effect	Source of Risk or Side Effect	Possible	Less Possible	Rare Events
Potential Risks Associated Study Enrollment & Study Procedures	Discomfort	Blood draw for lab test, ultrasound or MRI	X		
	Thrombophlebitis, bruising, bleeding, blood clot, Pre-syncope or Syncope (i.e. Fainting)	Blood draw for lab tests		X	
	Anxiety or Claustrophobia	MRI scan		X	
	Psychological Discomfort	Clinical Trial			X
	Infection	Blood draw for lab tests			X
	Allergic Reaction	MRI contrast			X
	Gadolinium contrast adverse reaction (i.e. Nephrogenic Systemic Fibrosis or severe skin reaction from contrast agent only reported in patients with kidney dysfunction)	MRI Contrast injection			X
	Confidentiality breach from Medical Records	Medical Record Keeping			X
	Groin/Anesthetic Injection/Neurologic Injury/	Pressure during arterial access and	X		
	Discomfort/Pain	after catheter removed at the leg/femoral artery site	X		
Risks of the PAE	Radiation Exposure Injury	PAE procedure			X
	Kidney Dysfunction	Contrast injected during procedure		X	
	Infection	PAE Procedure		X	

Procedure and Post-operative care	Adverse or Allergic Reaction	Intravenous contrast agent or medications administered as part of procedure or follow-up care (ie. MRI contrast)		X	
	Tissue damage to Skin, Muscle, Skin or other structure in legs and groin (Non-target Embolization)	PAE procedure			X
	Minor Bruising or Bleeding	PAE procedure			X
	Bleeding requiring Transfusion or surgery	PAE procedure			X
	Post Embolization Syndrome, including fever, malaise, headache, and myalgia (body aches)	PAE procedure		X	
	Internal bleeding, such as Gastrointestinal bleeding	Medications taken after the procedure (i.e. Ibuprofen)			X
	Infection	Catheter site in the leg/groin			X
	Arterial injury/trauma, laceration, bruising/pseudo aneurysm	Procedure/ Closure device (clip) on the artery			X
	Pulmonary embolism (clot in lung), Thrombophlebitis (clot in artery or vein)	PAE procedure			X

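### Criterion 3.2.11 admits anuric men on dialysis, who cannot give a meaningful IPSS, Qmax or PVR; the expected effect is very small

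*Combined protocol and SAP*

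**What the plan says.** Section 3.2.11 excludes men by serum creatinine (above 1.8 mg/dl) or by "glomerular filtration rate < 60 as approximated using serum creatinine levels) unless anuric and on dialysis". The closing words, "unless anuric and on dialysis", are an exemption: a man who would fail the kidney test is let in if he makes no urine and is dialysed. The protocol does not define anuria; I take it in its ordinary sense.

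The primary outcome in Section 2.3.1 is "Reduction in IPSS at 6-month follow-up". Section 2.3.2 adds quality of life, Qmax and PVR, prostate volume and percentage infarcted, all at 6 months, and adverse events at 3 months. The Section 4.3 schedule collects IPSS, Qmax and PVR at screening and at 3, 6 and 12 months.

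On imaging, Section 4.1.6 states "A MRI of the pelvis with and without contrast will be ordered", but waives this scan if a contrast-enhanced pelvic MRI exists from the previous 6 months. The Section 5.4 risk table describes the gadolinium reaction as nephrogenic systemic fibrosis or "severe skin reaction from contrast agent only reported in patients with kidney dysfunction", and classes it among rare events.

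**The concern.** The trial asks whether urinary symptoms after PAE are no worse than on medication. A man who produces no urine has no stream, no stopping and starting and no residual to report, so his IPSS says nothing on that question. The plan is otherwise careful here. Section 3.2.3 keeps out users of SGLT2 inhibitors because of the diuretic action of those drugs, and Section 3.2.13 keeps out bladder conditions that could confound the results. Men whose urine output is merely altered by a drug are excluded, while men with none are expressly admitted.

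At stake is a place in a 30-man study, used by someone whose primary outcome is either missing or uninformative and who cannot be replaced once treated.

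**Working it through.** **1. Can he be enrolled?**

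- 3.2.11 exempts him by name.
- 3.2.10, "Complete urinary retention", concerns urine that is made but not passed.
- 3.2.13, "Urethral strictures, bladder neck contracture, or other potentially confounding bladder pathology", concerns the bladder and urethra, not the absence of urine.
- 3.1.4, "Currently taking BPH medications including either alpha blockers, 5-alpha reductase inhibitors or the combination of both for no less than 6 months", makes him improbable but does not bar him.
- Section 3 sets no minimum IPSS, Qmax or voided volume.

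Nothing listed keeps him out.

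**2. Which outcomes could he supply?**

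| Outcome | Source | Usable? |
|---|---|---|
| IPSS | 2.3.1; items in 12.1 | No: the items concern emptying, frequency, stream, straining and the like |
| Qmax, PVR | 2.3.2 | No: nothing is voided |
| Prostate volume, percentage infarcted | 2.3.2 | Yes |
| Adverse events | 2.3.2 | Yes |

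**3. Does anything later correct for this?** Under Section 8.3, consent, eligibility and receipt of PAE make a subject evaluable, and he meets all three. Section 4.1.15 allows replacement only of men who withdraw before PAE. Section 4.2.2 counts a 6-month IPSS no higher than baseline as clinical success. If he scores 0 at both visits (assumed), 0 is not above 0 and he is a success. No rule for the outcomes of dialysis patients is given.

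**4. Size.** Share of places: 1/30 = 3.3%.

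The plan's own power figure reproduces and is not disputed on this point. Inputs from Section 8.2: SD 5.7 at both times, correlation 0.65, 30 pairs less 20% dropout, alpha 0.025 (taken as one-sided), decreases of 9.23 and 6.6.

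- SD of the difference = 5.7 × √(2 × (1 − 0.65)) = 4.769
- n = 30 × 0.80 = 24
- Effect = (9.23 − 6.6) + 10% of that = 2.63 + 0.263 = 2.893
- Paired t-test power (noncentral t) = 81.22%, against 81.2% stated

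This figure takes the margin as 10% of the 2.63-point difference. Section 8.3 instead sets it at 10% of the screening mean, and the illustration below follows Section 8.3.

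Suppose k of the 24 analysed men score 0 at both visits and the others have baseline mean B and true change 0. The documents give neither the zero scores nor B, so B is varied from 15 to 25. Then:

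- margin = 0.10 × B × (1 − k/24)
- SD of the difference = 4.769 × √(1 − k/24)
- for example, B = 15 and k = 1: margin 1.5 × 23/24 = 1.44, SD 4.67

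| Baseline mean B | k = 0 | k = 1 | k = 2 | k = 3 |
|---|---|---|---|---|
| 15 | 31.4% | 30.4% | 29.3% | 28.1% |
| 20 | 50.3% | 48.7% | 47.0% | 45.3% |
| 25 | 69.1% | 67.3% | 65.4% | 63.4% |

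The loss is about 1 to 2 percentage points per man. If the other men instead improve by 2.63 points, power for k = 0 to 3 is 98.2%, 97.7%, 97.0% and 96.1% at B = 15, a loss of less than 1 point per man. These are paired t-test approximations to the random effects model in Section 8.3.

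**The case against.** The strongest reply is that the clause will almost never operate. The study recruits men on BPH medication from urology and interventional radiology clinics, and a man who passes no urine is hardly a candidate for symptom relief. Screening obtains IPSS, Qmax and PVR unless they were done in the prior 3 months, so the problem should surface before PAE, while replacement is still possible. This stands as to frequency. It does not remove the mismatch, because no criterion is tied to those measurements and the text would still call him eligible.

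The exemption may also be deliberate: Section 5.4 lists kidney dysfunction from procedural contrast, and an exclusion meant to protect kidney function could exempt men with none left to protect. That is an inference, since the protocol gives no reason. Even so, it would not make the voiding outcomes measurable.

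Four stronger readings are tempting but not supported:

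- *That he yields no usable data.* Prostate volume, percentage infarcted and adverse events do not depend on voiding.
- *That he displaces 1 of 24 evaluable pairs (4.2%).* This holds only if he is scored and analysed. If his IPSS is missing, he is one of the 30 × 0.20 = 6 losses already allowed for.
- *That he adds a false clinical success.* The 0 and 0 scores are assumed, and the analysis plan in Section 8.3 does not test or tabulate clinical success; it models mean IPSS.
- *That he would necessarily have a study contrast MRI.* A recent scan waives the baseline one. Contrast at 6 months is only implied, by the perfusion aim in Section 4.1.1 and the infarct measurement in Section 8.3. The gadolinium reaction is disclosed, as rare.

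**Conclusion.** The point holds as a mismatch between a stated eligibility rule and what the trial measures. The exemption in 3.2.11 admits men who cannot give a meaningful primary outcome, and the evaluability and replacement rules would keep them in. The firm figure is 1 of 30 places (3.3%) per man enrolled. The power loss of about 1 to 2 points per man rests on assumed zero scores, an assumed baseline mean of 15 to 25 and no true change. Because enrolment is unlikely, the expected effect on the result is very small. This is a minor correction that does not threaten the primary analysis. The contrast question is a separate clinical matter, to be flagged for reconciliation only; it is not a ground for the change.

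**What to change.** Remove the exemption at the end of 3.2.11, giving as the reason that enrolled men must be able to supply IPSS, Qmax and PVR. If the sponsor wishes to keep it, Section 8.3 should state how the IPSS, Qmax, PVR and clinical success of such men are handled.

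Separately, the sponsor should reconcile the exemption with the contrast MRI in Section 4.1.6 and the gadolinium entry in Section 5.4. Which clinical rule should apply is not for this point to say.

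The cost is one deleted clause, submitted to the IRB as an amendment under Section 9.6, and a negligible loss of recruitment.

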The International Scientific Committee (SCI), under the patronage of the World Health Organization (WHO) and the International Union Against Cancer (UICC), recommends the use of only a single question to assess the quality of life. The answers to this question range from "delighted" to "terrible" or 0 to 6. Although this single question may or may not capture the global impact of benign prostatic hyperplasia (BPH) Symptoms or quality of life, it may serve as a valuable starting point for a doctor-patient conversation.

The SCI has agreed to use the symptom index for BPH, which has been developed by the AUA Measurement Committee, as the official worldwide symptoms assessment tool for patients suffering from prostatism.

The SCI recommends that physicians consider the following components for a basic diagnostic workup: history; physical exam; appropriate labs, such as U/A, creatine, etc.; and DRE or other evaluation to rule out prostate cancer.

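### Suspected but unconfirmed prostate cancer meets no exclusion (3.2.16), although suspected bladder cancer does (3.2.12), and the pre-PAE MRI carries no eligibility consequence

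*Combined protocol and SAP*

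**What the plan says.** All of the following is in the combined protocol and SAP.

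- **3.2, lead sentence:** "All subjects meeting any of the exclusion criteria at baseline will be excluded from study participation". The list that follows contains no criterion based on investigator discretion.
- **3.2.16 (prostate):** "Confirmed malignancy of the prostate or a history of prostate cancer".
- **3.2.12 (bladder):** "Confirmed or suspected bladder cancer as assessed based on patients' medical history or current hematuria".
- **3.2.13 (nearest neighbour):** "Urethral strictures, bladder neck contracture, or other potentially confounding bladder pathology".
- **4.1.6 (screening):** "A MRI of the pelvis with and without contrast will be ordered and obtained prior to visit 2", unless a contrast-enhanced pelvic MRI from the previous 6 months exists, in which case that one is used. The stated purpose is baseline evaluation of the prostate.
- **4.1.14 and 4.1.15 (removal and replacement):** a subject is withdrawn for a major complication that prevents completion of PAE or of follow-up, or leaves by his own choice. Replacement is limited to those who withdrew before PAE.
- **12.1 (IPSS appendix):** the text accompanying the questionnaire mentions "DRE or other evaluation to rule out prostate cancer" as part of a basic diagnostic work-up recommended to physicians.

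**The concern.** The two cancer criteria stand in the same list but use different standards. The looser one applies to the organ that is embolized. A man whose baseline MRI or existing chart raises an unresolved question of prostate cancer passes 3.2.16 as long as nothing has been confirmed and he has no such history.

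This is mainly a matter of patient safety: the procedure is meant to cause ischemia in the gland (4.1.2), and nothing in writing requires the question to be looked at first. It is also a matter of consistency. Recruitment runs at three sites (4.1.1), and without a written rule each site will settle the case in its own way.

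There is an analysis link too. Section 8.3 makes a subject evaluable if he consented, met the eligibility criteria and received PAE, so the wording of 3.2.16 also decides who counts as evaluable. Once treated, he cannot be replaced under 4.1.15.

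**Working it through.** No arithmetic applies. The plan states no figure on this point, and the point depends on none. The check is a reading of every place that could exclude, detect or remove such a man.

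**Step 1: compare the two criteria.**

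| | Bladder cancer (3.2.12) | Prostate cancer (3.2.16) |
|---|---|---|
| Confirmed disease | excluded | excluded |
| Suspected disease | excluded | not mentioned |
| History of disease | one of the grounds for suspicion | excluded if prostate cancer |
| Basis for judging suspicion | medical history or current hematuria | none given |

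The authors also use a suspicion standard elsewhere: 3.2.1 rules out suspected severe arterial calcification from the medical history when no prior imaging is held at the lead institution. So its absence from 3.2.16 does not follow from a general drafting rule.

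**Step 2: look for another criterion that closes the gap.**

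- 3.2.13 is limited to the urethra, bladder neck and bladder.
- 3.2.15 concerns previous pelvic radiation or radical pelvic surgery.
- 3.1.6 concerns life expectancy above 1 year.
- Section 3.0 describes subjects as men with BPH, which does not rule out a coexisting suspicion of cancer.

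None reaches suspected prostate cancer.

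**Step 3: look for a step between enrolment and PAE that closes it.**

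- In 4.1.6 the criteria are checked and consent is taken first. The MRI is then "obtained prior to visit 2 for baseline evaluation of the prostate", or an existing one is used. The image is therefore available before embolization, but no sentence ties its result to eligibility.
- 4.1.7 adds only a medication history questionnaire before the procedure.
- The time and events table in 4.3 lists the MRI and no other prostate cancer assessment.
- 4.1.14 gives no ground for removing a man because of a finding made before PAE.

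**Step 4: follow the case through.** A man with a suspicious baseline MRI, no confirmed malignancy and no history of prostate cancer meets no exclusion in 3.2, meets no removal criterion in 4.1.14, and is evaluable under 8.3 once treated. The gap holds on the text.

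**The case against.** The strongest case against runs as follows.

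**Clinical oversight exists.** Subjects come from urology and interventional radiology clinics, have had a pre-study work-up, and are seen by a co-investigator before PAE. A reader might infer from the criteria that a man with suspected prostate cancer will be embolized. The documents do not support that: nothing directs it, and clinical judgement may intervene. What remains is that no provision requires it to.

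**The MRI may already fall within the eligibility window.** The exclusions apply at baseline, and 4.1.6 describes the MRI as a baseline evaluation. For some men a scan from the previous 6 months exists before enrolment. This is a fair reading of timing, and it stands. It does not close the gap, because a suspicious MRI reviewed against 3.2.16 as now worded still meets no exclusion.

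**The appendix is not a study requirement.** A reader might take the line in 12.1 as proof that the protocol contradicts itself. It is general background printed with the IPSS form and reports a committee's advice to physicians. It neither proves a contradiction nor fills the gap.

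**No size is shown.** This stands in full. A reader might want to attach a count, or note that each affected man is 1/30 = 3.3% of the planned sample. The documents give no prevalence of suspicious findings. Harm to the results would also need further steps: confirmation after PAE, then cancer treatment or departure before month 6. A man with a gland of at least 50 g on BPH medication may still have symptoms from BPH. No bias in the 6-month IPSS comparison can be derived from this.

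**How far to pursue suspicion before PAE is a clinical decision.** This also stands. The request is to reconcile the criteria, or give the reason for the difference, and write the handling down; the definition of suspicion belongs to the investigators.

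**Conclusion.** The gap is real and worth correcting. Criterion 3.2.16 is narrower than 3.2.12 with no reason given, no other criterion or removal rule covers suspected prostate cancer, and the MRI that must be available before Visit 2 has no stated consequence for eligibility. The importance lies in patient safety and in uniform handling across sites.

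The conclusion rests on the text alone and on one reading: that the criteria listed in 3.1 and 3.2, with 4.1.14, are the complete written rules for entry and removal. It does not depend on how common suspicious findings are. Its size cannot be given, and no effect on the primary non-inferiority test is asserted.

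**What to change.** 1. **3.2.16 and 3.2.12.** Reconcile them so that prostate cancer is held to the same confirmed-or-suspected standard as bladder cancer, or state why it differs. If the standard is aligned, the investigators should define how suspicion is judged from the baseline MRI and results already in the chart, as 3.2.12 does for the bladder. Without a stated basis, sites could apply it differently, and men with fuller charts could be excluded more readily.
2. **4.1.6.** State that the MRI, whether new or from the previous 6 months, is reviewed against 3.2.16 before PAE.
3. **4.1.14 and 4.1.15.** Add that a man found ineligible before PAE is removed and may be replaced. At present 4.1.14 gives no such ground, and 4.1.15 speaks of subjects who withdrew, so replacing a man removed by the investigator is only an inference.

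Cost: short edits in four sections and an agreed definition from the investigators. No new test is needed, because the MRI is already required and other results would be used only where they exist. The downside is a few more screen failures before PAE, which the amended 4.1.15 would allow to be replaced.
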